7.4. EXTRA VISITS

In addition to the visits provided here, **extra visits may be made to** perform procedures indicated by the Principal Investigator prioritizing the safety of the visiting participant.

7.5. VIEWING WINDOW

To be eligible to participate in the study, among the proposed inclusion criteria is the presence of a positive diagnostic test for SARS-CoV-2 by molecular amplification of the virus in a respiratory sample (nasopharyngeal, oropharyngeal, lower respiratory tract, e.g.: sputum) collected <96 hours before randomization. For this reason, the time between screening and randomization should not exceed 4 days.

To attend the end-of-follow-up visits (**D28 and D60**) participants will have the possibility to **advance or delay by up to three days** from the initially scheduled date.

8. ADVERSE EVENT REPORTING

Adverse Event (AE), according to ANVISA, means "any adverse medical occurrence in a patient or clinical trial participant to whom a pharmaceutical product has been administered and that does not necessarily have a causal relationship to the treatment. As a result, an AE can be any unfavorable and unintended sign, symptom, or disease (including results outside the reference range), associated with the use of a product under investigation, whether related to it or not." The adverse event can be related to the following situations:

- Exacerbation of pre-existing medical conditions and/or the original disease (including symptoms, signs, laboratory abnormalities);
- Any new adverse events or new adverse medical conditions (including symptoms, signs, newly diagnosed diseases);
- Abnormal values of clinically significant laboratory or imaging tests or results that are not caused by concomitant diseases.

8.1. SERIOUS ADVERSE EVENT (EAG)

According to ANVISA's definition, a serious adverse event is "one that results in any drug experience [...], occurring at any dose and resulting in any of the following outcomes."

- Death;
- Imminent threat to life;
- Persistent or significant disability/disability;
- Inpatient hospitalization or prolonged hospitalization;
- Congenital anomaly or birth defect;
- Any suspected transmission of an infectious agent through a drug;
- Other clinically significant events: events that can lead to one of the above, including but not limited to the following events, such as allergic bronchospasm requiring intensive treatment in the emergency room or at home, blood system cachexia or seizures not requiring hospitalization, potential drug-induced liver injury, spread of pathogens (non-pathogenic or pathogenic) via the study drugs, pregnancy, overdose, secondary tumors, etc, are generally considered serious, although they may not lead to death or hospitalization.

The Principal Investigator should provide the EAG severity criteria, based on the study protocol and their own medical judgment, on the eCRF and the results of the evaluation of the expected occurrence of the EAG and the correlation (cause and effect) with the study drug.

If the causality assessment performed by the Principal Investigator is missing or cannot be obtained, the sponsor will make the judgment and provide the final assessment, which will subsequently be confirmed by the Principal Investigator. If the Principal Investigator cannot determine whether or not the AE belongs to an SAE, then it will be considered an SAE until its nature is proven.

When any SAE occurs in the study, whether related to the experimental drug or not, the investigators should provide immediate assistance.

Planned or elective hospital admissions, for administrative reasons (such as annual physical exam) or prolongation of length of stay unrelated to worsening AEs, will not be considered SAEs. **The following situations will not be reported as SAE:**

- Treatments/procedures for a pre-existing condition/illness reported in the screening period;
- Hospital readmission due to the original disease with no new AE and no exacerbation of the original disease (such as verification of laboratory abnormalities that have persisted so far);
- Invasive (such as surgery) and non-invasive diagnostic or therapeutic procedures should not be reported as an EAG. However, it should be reported when the condition that led to that operation meets the definition of AE. For example, acute appendicitis that occurred during the AE monitoring period should be reported as an AE and therefore an appendectomy should be recorded as the treatment method for this AE.
- AEs leading to hospitalization or prolonged hospitalization in clinical trials should be considered as AEs. The following inpatient situations are not considered as AEs: rehabilitation facilities; nursing home; routine emergency room admission; same day surgery (as outpatient/same day/outpatient surgery).

Hospitalization due to symptoms and signs of disease progression during the trial should not be reported as an SAE, while death due to disease progression (including signs and symptoms of progression) should be reported as an EAG. Events that caused death should be reported as an EAG, for example, if cancer led to the participant's death during the trial.

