11.3. METHOD OF STATISTICAL ANALYSIS

All statistical tests will be two-sided tests.

- If the p-value is ≤0.05, it is considered that there is statistical significance in the test (unless otherwise specified).
- The quantitative indices describe the mean value, standard deviation, median, minimum value, maximum value, lower quartile (Q1), upper quartile (Q3) to be calculated, and the rank indices describe the frequency and percentage of cases.
- Comparison of the two groups under general conditions will be analyzed with appropriate methods according to the types of indicators. Student's ttest or Mann-Whitney test will be used to compare the groups for quantitative data. Chi-square test or Fisher's exact test will be used for categorical data.
- The selected cases should be grouped and at the end of the study determine the three analysis data sets (FAS, PPS, SS).
- For the analysis of demographic information and baseline eigenvalues, the mean value, standard deviation, quartiles, minimum value and maximum value should be calculated for numeric variables. For categorical data, frequency and percentage will be calculated.
- For analysis of medication and drug combination adherence one should calculate the percentage of individuals whose medication adherence is at

least 80-100%. An analysis of the classification of the combination of drugs should also be done.

• For analysis of the primary effectiveness indicator:

Primary Goal

To evaluate the **efficacy and safety of** AZVUDINE (FNC) versus placebo in patients infected with moderate to severe stage SARS-COV-2;

Analysis method:

For the efficacy analysis a logistic regression model will be used with the dependent variable "The proportion of participants with clinical improvement [Period: until D15, approximately 14 days]" and independent variables allocation group, AZVUDINE (FNC) or PLACEBO. For the Safety analysis a logistic regression model will be used with the dependent variable "occurrence of serious adverse events" and independent variables allocation group, AZVUDINE (FNC) or PLACEBO. As a support analysis, with exploratory character, both for efficacy and safety, covariate models will be built as well as other variables that present, in the univariate analysis, statistical significance.

Secondary objective

To evaluate the **clinical outcome** between the AZVUDINE (FNC) group versus placebo in patients infected with moderate to severe stage SARS-COV-2;

Analysis method:

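### Section 8.1 gives conflicting instructions on whether an adverse event that causes or prolongs hospitalisation is an SAE, so the SAE count and its reporting depend on which line is followed

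*Protocol*

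**What the plan says.** Protocol section 8 counts as an adverse event "Exacerbation of pre-existing medical conditions and/or the original disease (including symptoms, signs, laboratory abnormalities". Worsening COVID-19 is therefore an AE.

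Section 8.1 (which uses EAG and SAE for the same thing) then gives five relevant statements, in this order:

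- The seriousness criteria include "Inpatient hospitalization or prolonged hospitalization".
- A longer stay is carved out only in a limited case: "prolongation of length of stay unrelated to worsening AEs, will not be considered SAEs".
- A list opens with the words "The following situations will not be reported as SAE". One of its first bullets is "Hospital readmission due to the original disease with no new AE and no exacerbation of the original disease".
- A later bullet of the same list reads "AEs leading to hospitalization or prolonged hospitalization in clinical trials should be considered as AEs". It goes on to name inpatient settings that do not count, such as rehabilitation, nursing homes and same-day surgery.
- After the list comes "Hospitalization due to symptoms and signs of disease progression during the trial should not be reported as an SAE". The same sentence makes death from progression reportable as an SAE.

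Section 11.3, under the primary objective, specifies a logistic regression of SAE occurrence on allocation group. Section 7.1.2 lists the frequency and intensity of SAEs among the secondary outcomes. Section 8.10 requires the sponsor to be told of an SAE within 24 hours. On study treatment, the Synopsis says it will be stopped early if an SAE occurs, and section 5.1.1 says it may be.

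**The concern.** Participants are hospitalised patients, so the initial admission cannot mark an event as serious. A prolonged stay, or a readmission after discharge, is a natural non-fatal route to seriousness in this trial. These are the two situations on which section 8.1 gives conflicting instructions.

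More than labelling depends on the answer. An event classed as an SAE enters the safety model, must reach the sponsor within 24 hours and bears on whether treatment stops. Recurring SAEs suspected of being drug-related are also the stated ground for full unblinding (section 5.4.3). An event classed only as an AE has no fixed deadline beyond timely notice (section 8.10), or 7 days if it is of special interest (section 8.3). A statistical analysis plan cannot repair this afterwards if events were never recorded as SAEs.

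**Working it through.** No arithmetic applies. The check is whether one event, taken through each line of section 8.1, gets one answer.

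| Event | Seriousness criterion | Limited exemption | Later line | Consistent? |
|---|---|---|---|---|
| A. Worsening dizziness keeps an inpatient in hospital longer | SAE | Longer-stay exemption does not apply: the stay is related to a worsening AE | Bullet in the not-SAE list: an AE | No |
| B. Discharged participant readmitted with worsening COVID-19 | SAE (section 8 makes the worsening an AE; it led to hospitalisation) | Readmission exemption does not apply: there is an exacerbation | Progression sentence: not an SAE, if the exacerbation counts as progression | No, if exacerbation is progression |
| C. Readmission for the original disease, no new AE, no exacerbation | Would be met on its face | Exempt | Nothing contrary | Yes |
| D. Death from disease progression | SAE | None | Progression sentence: SAE | Yes |

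**Event A** is a direct conflict. The criterion and the limited carve-out agree with each other: a stay lengthened by a worsening AE is serious. The bullet stands under a heading that says its contents are not reported as SAEs, and it assigns the same event to the AE category.

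**Event B** is a conflict partly by implication. The readmission bullet is limited to cases without exacerbation, and that limit has a purpose only if cases with exacerbation are treated differently. The progression sentence has no such limit and exempts every non-fatal hospitalisation for progression. The two agree only if progression and exacerbation are different things, and the protocol defines neither. The progression sentence also mentions hospitalisation but not prolongation, so it does not say how to class an inpatient whose stay is extended by worsening COVID-19.

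**Events C and D** show the limits of the problem: the rules agree on uncomplicated readmission and on death.

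The size of the effect would need expected rates of SAEs, prolonged stay or readmission in this population. The protocol gives none, so no count of affected events is offered.

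**The case against.** **The bullet may be a wording slip.** Taken alone it says that AEs are AEs, which makes sense only if the second term was meant to be SAEs. What follows, a list of settings that do not count, suits a rule with exceptions. The preceding bullet also contains an instruction to report, so the heading does not turn every sentence below it into an exemption. Every SAE is also an AE, so the label does not strictly deny seriousness. This is a plausible account of the intent and it stands as such. It does not remove the defect, because staff work from the words, and where the bullet sits supports the non-serious reading.

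**There is a default.** Section 8.1 has an event treated as an SAE when the investigator cannot decide. That softens the problem for anyone who notices the conflict. It does not help someone who reads the not-SAE list as a clear instruction and so is not in doubt.

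**Exempting progression is legitimate.** This stands. Leaving progression of the trial disease out of SAE reporting is a design choice, and exempting one case does not strictly state that its opposite is reportable. What remains is the missing definition and the missing order of precedence.

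**Other outcomes capture worsening.** Intensive care, invasive ventilation, length of stay and mortality are separate secondary outcomes, so clinical worsening would not disappear from the trial. The SAE count and the expedited reporting would still be affected.

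Four stronger readings are tempting but not supported:

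- That SAE occurrence is a primary endpoint. The only listed primary endpoint is improvement in clinical status; SAEs are a secondary outcome that is also modelled under the primary objective.
- That the ambiguity favours azvudine. The trial is double-blind, and nothing in the text makes misclassification differ by arm.
- That a given number of events per arm would change class. Any such figure would rest on invented rates.
- That a stay prolonged by raised transaminases shows the conflict cleanly. Section 8.1 separately treats potential drug-induced liver injury as generally serious, so such a case may be an SAE by another route.

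**Conclusion.** The point holds as a contradiction in the current text of section 8.1. On hospitalisation or prolonged stay caused by an AE, the conflict is direct, and the bullet is wrong as written, whether or not it is a slip. On hospitalisation for worsening COVID-19, the conflict is partly by implication and rests on progression and exacerbation overlapping, which the protocol neither states nor rules out.

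The consequence is that SAE occurrence, its 24-hour notification and the treatment provisions tied to it depend on which line staff follow. The trial has a single site, so one reading adopted there could shift the whole SAE count, and mixed use would add misclassification. The size cannot be estimated from the protocol, and the conclusion does not depend on it.

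**What to change.** Reconcile sections 8 and 8.1 to one rule:

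1. Correct the bullet on AEs leading to hospitalisation, or move it out of the not-SAE list, so that it no longer conflicts with the stated seriousness criterion. Keep the inpatient settings that do not count as a separate exclusion if that was the intent.
2. State one rule for hospitalisation, readmission and prolonged stay due to worsening COVID-19. If progression is to be exempt, define it, say how it differs from exacerbation, and make the exemption agree with the limit in the readmission bullet.

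Which rule to adopt for disease progression is for the sponsor to decide. Recording such events as SAEs with a progression flag, and running the safety model with and without them, is one possible form, but reconciling the text does not require it.

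The cost is protocol wording and possibly a few more SAE forms. No extra visits or participants are needed.

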8.2. SUSPECTED UNEXPECTED SERIOUS ADVERSE EVENT (SUSAR)

Unexpected serious adverse reaction whose nature, severity, consequence or frequency is not consistent with the expected risks described by the information in the most current investigator's brochure. All unexpected serious adverse reactions occurring during the clinical trial that are definitely related to or suspected of the investigational product are SUSAR. The assessment of SUSAR should be performed considering the following aspects:

- If the AEs are listed in the investigator's brochure (BI);
- Although the AEs are listed in the BI, whether or not their severity is consistent with what is described in the BI;
- Although the adverse events are listed in the BI, the frequency of occurrence is higher than described in the BI;
- Other situations.

.

8.3. ADVERSE EVENT OF SPECIAL INTEREST

According to the results of the current clinical trials, the adverse events that may be related to the product are:

- Dizziness;
- Headache;
- Decreased phosphorus in the blood;
- Increased alanine aminotransferase;
- Increased aspartate aminotransferase;
- Increased total bilirubin;
- Increased y-glutamyl transferase;
- Decreased neutrophils;
- Increased glucose in the blood.

•

However, according to the AE incidence data reported in the clinical

development phases of the FNC performed earlier, among the AEs already described, AEs of special interest will be considered:

- Changes in markers of liver function ¹⁵:
 - Elevation of AST/TGO above reference values.
 - Elevation of ALT/GTP above reference values.
- Changes in markers of renal function:

Decrease in estimated Glomerular Filtration Rate (eGFR) <30mL/min.

Grade 3 AEs related to dizziness, due to increased risk of falling.

The Principal Investigator should classify the degree of intensity and correlation (cause and effect) between the test drug and the AE of Special Interest, based on the trial protocol and his own medical judgment, and record it in the specific eCRF. The sponsor should be notified within 7 days about the occurrence of AE of Special Interest.

8.4. AES MONITORING

If there is any abnormality or AE, serious or not, unexpected or not, during or after treatment, follow-up should be made until the clear outcome of recovery or stable status. Individuals with AEs that develop after discharge should contact the Principal Investigator or his/her team to determine what action should be taken for that individual to fully recover from the AE.

After the end of the trial, if participants have AEs again that are or could be related to the use of the investigational drug, the PI should inform the sponsor in time.

For all EAGs (including those still in the developmental stage after the end of the trial and until the end of the last patient's follow-up), the Principal Investigator should follow the patient until recovery, stabilization, or death to ensure that all

¹⁵ TGO Adult 12 to 46 U/L; TGP Adult 03 to 50 U/L (Source: Hermes Pardini Institute)

problems are resolved. Until the EAG has been resolved, the Principal Investigator should keep the sponsor informed. Detailed follow-up information should be provided, such as whether or not special treatment is needed after the trial, whether or not hospitalization is required, etc.

8.5. AF INTENSITY

The intensity of AE in this study is classified according to the World Health Organization criteria, adopted by ANVISA:

- **Mild:** present less than 25% of the time, with an intensity that a person can tolerate and that has rarely happened since the start of treatment.
- Moderate: present less than 50% of the time, with an intensity that interferes with the individual's day-to-day activities and has happened occasionally since the beginning of treatment.
- **Severe:** present more than 50% of the time, with an intensity that partially alters the individual's daily life and has happened frequently since the beginning of treatment.
- **Complete impairment:** present more than 95% of the time, with an intensity that completely alters the individual's daily life, and has occurred every day since the start of treatment.
- **Not specified:** not enough information to specify the intensity.
- **Not applicable:** it is inappropriate to use a gradation (e.g. menstrual functions).

8.6. CASUALITY BETWEEN EAS AND DRUGS IN THE STUDY

All AEs, whether serious or not, unexpected or not, should be reviewed by the Principal Investigator for correlation analysis with study drugs, in accordance with 11. The following factors should be taken into consideration when analyzing the correlation between AEs and study drugs:

• If there is a reasonable time sequence between the time of action of the

drug and the AEs, and it was possible to observe a plausible relationship between the administration of the drug and the event that occurred;

- Whether AEs can be explained by the original disease, by another intervention, or by environmental factors;
- Whether there was a response, pharmacological or pathological, after discontinuation or dose reduction of the study drug;
- If the same AE reappeared after resumption of the suspected drug, whether re-exposure of the participant to the study drug was possible;
- Whether the clinical or pathological manifestation of the AE is consistent with knowledge of the pharmacological and toxicological classification of the known study drug;
- If the data about the EA is clear, complete and traceable.

CORRELATION	CRITERIA
Sure/Defined	 There is a reasonable time sequence between the AE and thedrug; EA cannot be explained by other factors; There was a response after dose withdrawal or reduction; The same AE reappeared after resumption of the drug, if re-exposure was possible; The AE is consistent with the medicine.
Probable	 There is a reasonable time sequence between the AE and thedrug; Unlikely that the AE is attributable to other factors; There was a response after dose withdrawal or reduction; No re-exposure of the drug was possible or there is no clear information.

AZVUDINE Clinical Trial Do	esign
Possible	 There is a reasonable time sequence between the AE and the drug; AE can also be attributed to other factors; There is no clear information about the response after dose withdrawal or reduction.
Unlikely	 There is no clear sequence of reasonable time between the EA and the drug; AE can also be attributed to other factors;
Conditional/Unclassified	 There is no time sequence between the AE and the drug; The data is not clear for; Additional data is under investigation
Inaccessible/Unclassifiable	 The narrative of the account suggests an EA; The information is insufficient or contradictory; The data cannot be supplemented or verified.

Table 11: Causality relationship between AEs and study drugs.

8.7. AE COLLECTION AND REGISTRATION

Any information relevant to the trial should be recorded from the first administration to the end of follow-up. AEs will be monitored throughout the study and the Principal Investigator, or someone deligated by him, will be responsible for recording all adverse medical events observed during the study, in detail, in the source documents and in each participant's eCRF, during the study period from the first dose to the end of follow-up, regardless of severity and causal relationship to the study drug.

All SAEs must also be recorded in eCRF as soon as they occur, and the information provided in the SAE report form must be consistent with the event-related data that is recorded in eCRF. All AEs, SAEs and special interest AEs must include the following content in detail:

• **Description:** Events should be described in medical terms, rather than the words used to record the participants' reports in the original document. If

applicable, symptoms, signs, laboratory abnormalities, and diagnosis should be included. If the same AE occurs more than once, in the same participant, and the participant recovered from both events, the AE should be recorded twice.

- Date of occurrence: the date when the AE first occurred in the participant or
 the date when the symptoms related to the AE occurred should be recorded. If
 the AE is the test result of an abnormal laboratory test or test with clinical
 significance, the date of occurrence is the date the test was performed.
- Date of result: the date of resolution of the AE-related symptoms should be recorded.
- AE intensity and severity: classified as: (1) mild, 2 (moderate), 3 (severe) or 4 (complete/severe impairment). ¹⁶
- Causal relationship between AE and study drugs: as per Table 5.
- Measures for the study drug: It should be recorded whether the participant
 continued using the drug or had to stop using it as a result of the AE or SAE. If
 the reaction occurred after the end of treatment, this item does not apply.
- Measures for AE: It should be recorded what measures were taken to solve the
 AE, such as drug therapy and/or non-drug therapy, hospitalization, surgery,
 among others. If no action was taken, this fact should be reported.
- **Outcome:** the disappearance of signs or symptoms; recovery with sequelae; stability; worsening; death; or loss to follow-up must be recorded.
- **Significant AE:** refers to any obvious AE, hematologic, or other laboratory test abnormality that needs targeted clinical interventions (such as drug withdrawal, dose reduction, and/or routine treatment), except for SAE.

If an AE or SAE occurs during the trial, regardless of whether it is related to the study drug or not, the investigators should immediately take appropriate treatment measures to ensure the safety of the participants.

¹⁶ Manual for adverse event reporting and safety monitoring in clinical trials / Brasília. Anvisa, 2016

8.8. EVALUATION OF ABNORMALITIES OF CLINICAL LABORATORY TESTS AND OTHER ABNORMALITIES CONSIDERED AS EA

Laboratory test abnormalities without clinical significance are not recorded as AE or SAE. Laboratory test abnormalities with clinical significance (flagged as "abnormalities with clinical significance", such as clinical blood routine, blood biochemistry, etc.) and other abnormalities (such as ECG, vital signs), that meet the definition of AE or EAG, upon the principal investigator's evaluation and judgment, or that require individuals to receive specialized routine treatment, should be recorded as AE or SAE.

If laboratory abnormalities are part of the syndrome, record the results of the syndrome or diagnosis (e.g., anemia) rather than the results of the laboratory tests (i.e., reduced hemoglobin).

